11.2.2 Calculation of exposure adjusted incidence and event rates

The EAIR is defined as the number of subjects (n) with a specific TEAE adjusted for the exposure and will be scaled to 100 subject-years:

$$EAIR = 100 \times \frac{n}{\sum_{i=1}^N T_{Exp,i}} \quad [13]$$

In the above equation, N is the total number of subjects at risk (in each treatment group) and $T_{Exp,i}$ is the time at risk for subject i , expressed in years. Subject time at risk represents the time a subject was at risk for having a TEAE calculated as follows:

- For subjects experiencing the specific TEAE the time at risk ($T_{Exp,i}$) is calculated from the time of the first dose to the onset of the TEAE. If a subject has multiple events, the time at risk is calculated relative to the first occurrence of the TEAE being considered.
- For subjects who do not experience the specific TEAE the total time at risk ($T_{Exp,i}$) is calculated as described in [Section 11.1.3](#).

Exact Poisson 95% CIs (lower confidence limit [LCL], upper confidence limit [UCL]) for the EAIR will be calculated using the relationship between the Poisson and the chi-square distribution (Fay and Feuer, 1997):

$$LCL = \frac{\chi_{2n, \frac{\alpha}{2}}^2}{2}, \quad UCL = \frac{\chi_{2(n+1), 1 - \frac{\alpha}{2}}^2}{2} \quad [14]$$

where n is the number of subjects with the specific TEAE for the incidence rate of interest and is the basis for the number of the degrees of freedom for the chi-square quantile. The LCL and UCL calculated above will be scaled to the number of subject-years by dividing these by the total exposure at risk for each treatment group ($\sum_{i=1}^N T_{Exp,i}$).

The EAER is defined as the total number of TEAEs (including repeat occurrences in individual subjects) divided by the total time at risk scaled to 100 subject-years:

$$EAER = 100 \times \frac{n_{AE}}{\sum_{i=1}^N T_{Risk,i}} \quad [15]$$

where n_{AE} is the total number of TEAEs and $T_{Risk,i}$ is the time at risk for subject i , expressed in years (calculated as described in [Section 11.1.3](#)).

No confidence intervals will be computed for EAER.

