11.1.3 Subject time at risk

The subject time at risk represents the time a subject was at risk for having an AE and will be used to calculate the exposure adjusted incidence rate (EAIR) and exposure adjusted event rate (EAER) as described in [Section 11.2](#).

The subject time at risk (days) will be calculated as follows:

$$\text{Time at risk} = (\text{Date of Last Dose} - \text{Date of First Dose}) + 140 \quad [11]$$

In cases where the last clinical contact or last visit occurs prior to completion of the SFU period, the subject time at risk is calculated as follows:

$$\text{Time at risk} = (\text{Date of Last Contact} - \text{Date of First Dose}) + 1 \quad [12]$$

This will apply for the following:

- For subjects entering the extension study the date of last contact (in PS0016) refers to the date of the visit at which they enter the extension study (ie, Week 20, 24, 28 or 36)
- For subjects that discontinue prematurely (ie, and no SFU data are available), the date of final contact refers to the date of the latest contact with the subject during the study after

which no further information or data are available. This will be reported on the study termination page of the CRF.

- For subjects that have died during the study the date of last contact refers to the date of death
- Subject-years at risk is defined as the subject time at risk divided by 365.25. The days at risk and subject-years at risk will be listed together with the drug administration information (Section 11.1.1).

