11.2.3 Presentation of adverse events

An overview of the number and percentage of subjects who experience TEAEs will be presented by treatment group (including All Subjects), based on the SS. This tabulation will include the number and percentage of subjects with any TEAEs, serious TEAEs, related TEAEs, discontinuation due to TEAEs, severe TEAEs, AEs leading to death and TEAEs leading to death; event counts will also be included. The tabulation will be repeated for Treatment Period TEAEs and Overall TEAEs.

In addition, the following summaries will be presented by treatment group (including All Subjects), SOC, high level term (HLT) and PT, based on the SS:

- Incidence of TEAEs during Treatment Period
- Incidence of TEAEs Overall
- Incidence of serious TEAEs during Treatment Period
- Incidence of serious TEAEs Overall

-
- Incidence of non-serious TEAEs during Treatment Period
 - Incidence of non-serious TEAEs Overall
 - Incidence of TEAEs during Treatment Period by relationship
 - Incidence of TEAEs Overall by relationship
 - Incidence of TEAEs during Treatment Period by maximum relationship
 - Incidence of TEAEs Overall by maximum relationship
 - Incidence of TEAEs during Treatment Period by maximum intensity
 - Incidence of TEAEs Overall by maximum intensity
 - Incidence of fatal TEAEs during Treatment Period by relationship
 - Incidence of fatal TEAEs Overall by relationship
 - Incidence of non-serious TEAEs during Treatment Period by relationship
 - Incidence of non-serious TEAEs Overall by relationship
 - Incidence of serious TEAEs during Treatment Period by relationship
 - Incidence of serious TEAEs Overall by relationship
 - Incidence of non-serious TEAEs during Treatment Period above threshold of 5% of subjects
 - Incidence of non-serious TEAEs Overall above threshold of 5% of subjects
 - Incidence of non-serious TEAEs during Treatment Period above threshold of 5% of subjects by relationship
 - Incidence of non-serious TEAEs Overall above threshold of 5% of subjects by relationship
 - Incidence of TEAEs during Treatment Period by SOC and PT (including the number and percentage of subjects and individual subject numbers/reported terms for each PT stratified by intensity, relationship and seriousness)
 - Incidence of TEAEs (including all TEAEs during Treatment and Post-Treatment Periods) by SOC, HLT and PT and including the EAIR and EAER calculated as described in [Section 11.2.2](#)

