 - Incidence of TEAEs (including all TEAEs during Treatment and Post-Treatment Periods) by SOC, HLT and PT and including the EAIR and EAER, stratified by overall ADA status (positive/negative)

In addition, separate AE summaries by treatment group, SOC, HLT and PT (including all TEAEs during Treatment and Post-Treatment Periods combined) will be included for the following AEs of special monitoring (AESM):

- Major cardiovascular events
- Serious infections, including opportunistic infections and tuberculosis (TB)
- Malignancies including lymphoma

- Cytopenias
- Neuropsychiatric events (in particular, depression and suicide)
- Inflammatory bowel disease
- Anaphylactic reaction (hypersensitivity and anaphylactic reactions)
- Hepatic events and drug-induced liver injury

All summary tables (including those for AESM) will contain the number and percentage of subjects and the number of events where applicable. A subject who has multiple events in the same SOC, HLT and PT will be counted only once in the subject counts but all events will be included. In addition, for all tabulations of AESM, the EAER and EAIR will be reported.

The criteria for identifying AESM and additional criteria for reporting AESM are provided in [Section 14.6](#).

In summaries including relationship to IMP, the following relationship categories will be included:

- Related
- Not related

Subjects who experience the same event multiple times will be included in the most related category for tabulations by maximum relationship. Events with missing relationship will be considered as 'Related' for summary purposes but shown as missing in the data listings.

In summaries including intensity, the following categories will be summarized:

- Mild
- Moderate
- Severe

Subjects who experience the same event multiple times will be included in the most severe category for tabulations by maximum intensity. Events with missing intensity will be considered as severe for summary purposes. All data will be presented as recorded in the database for the listings.

Adverse event summaries will be ordered by alphabetical SOC, alphabetical HLT within SOC and decreasing frequency of PT in the 'BKZ 320mg' (Treatment arm B) column for tables including event counts. For tables including only number and percentage of subjects, summaries will be ordered by alphabetical SOC, alphabetical HLT within SOC and decreasing incidence of PT within HLT and SOC in the 'BKZ 320mg' (Treatment arm B) column.

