14.6.2 Serious infections, including opportunistic infections and tuberculosis

14.6.2.1 Serious infections

Serious infections are based on MedDRA classification using the SOC = ‘Infections and Infestations’. Such events will be included in the tabulations of SAEs and no separate summary tabulations will be presented.

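### The exact Poisson limits for the EAIR are not multiplied by 100, so as written they are per 1 subject-year beside an estimate per 100 subject-years

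*SAP*

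**What the plan says.** SAP Section 11.2.2 describes the EAIR as the number of subjects with a given TEAE, "adjusted for the exposure and will be scaled to 100 subject-years". Equation [13] is 100 × n divided by the sum of T_Exp,i, where T_Exp,i "is the time at risk for subject i , expressed in years".

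The section then specifies exact Poisson 95% confidence limits for the EAIR. Equation [14] gives them as half a chi-square quantile: 2n degrees of freedom for the lower limit and 2(n+1) for the upper. Neither contains exposure or a factor of 100. One scaling instruction follows: "The LCL and UCL calculated above will be scaled to the number of subject-years by dividing these by the total exposure at risk".

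SAP Section 11.2.3 uses these rates in the overall TEAE table, "including the EAIR and EAER calculated as described in" Section 11.2.2. It also calls for them in the table stratified by ADA status and in the tables for adverse events of special monitoring (AESM): "for all tabulations of AESM, the EAER and EAIR will be reported". Sections 11.2.3 and 14.6 add no other scaling rule. The EAER in equation [15] carries its own factor of 100 and has no interval.

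**The concern.** The estimate and its limits are on different scales. The section writes the 100 explicitly in equations [13] and [15] but leaves it out of the interval step. Programmers working independently from the text could all produce the same wrong limits and agree with each other.

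Incidence of adverse events is the primary safety variable (Protocol Section 4.1.4). Subjects can leave for the extension study from Week 20, so follow-up is unequal, and SAP Section 11.2.1 treats the EAIR and EAER as the summaries that adjust for individual exposure. For an event seen in no subject of an arm, which is likely with planned arms of 30 and 15, the upper limit is the only information on what rate can be ruled out. As written, it would suggest that far lower rates had been excluded than the data support.

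**Working it through.** The SAP gives no worked EAIR or interval, so there is no figure to reproduce. The check is of the formulas.

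**Inputs from the documents**
- EAIR = 100 × n / T, where T is the sum of T_Exp,i in years (SAP 11.2.2, equation [13]).
- Count limits from equation [14]: L(n) = χ²(0.025; 2n)/2 and U(n) = χ²(0.975; 2(n+1))/2. L(0) is taken as 0, because the lower quantile then has zero degrees of freedom.
- Limits as written: L/T and U/T.
- Time at risk: (last dose − first dose) + 140 days under equation [11], or (last contact − first dose) + 1 under equation [12]. "Subject-years at risk is defined as the subject time at risk divided by 365.25" (SAP 11.1.3).
- Planned arms of about 30 and 15 (SAP 2.3).

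**Step 1. Is equation [14] right for the count?** Yes. For n = 1, 3, 5 and 10, P(X ≥ n | L) and P(X ≤ n | U) are both 0.025; for n = 0 the upper tail is also 0.025. The formula and the denominator are sound. Only the multiplier is missing.

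**Step 2. Size of the error.** Limits on the EAIR scale are 100L/T and 100U/T. Their ratio to the written limits is (100L/T)/(L/T) = 100, and the same for U. This needs no assumption about n or T.

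**Step 3. Can the written interval contain its estimate?** That would need U/T ≥ 100n/T, that is, U(n) ≥ 100n. But U(1) = 5.57 against 100, U(2) = 7.22 against 200, and U(45) = 60.2 against 4500. Over n = 1 to 45 the largest U(n)/n is 5.57, at n = 1. The interval therefore excludes its estimate for every n ≥ 1. For n = 0 it contains 0, with upper limit 3.689/T instead of 368.9/T.

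**Step 4. Illustration.** Assumptions: planned arm sizes, visit windows ignored, and exposure not cut at event onset.
- Full follow-up: (112 + 140)/365.25 = 0.690 years per subject, so arm A has 30 × 0.690 = 20.7 and arm B 15 × 0.690 = 10.3 subject-years.
- All enter the extension at Week 20: (140 + 1)/365.25 = 0.386 years per subject, so arm A has 11.6 and arm B 5.8 subject-years.

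| Arm | T (subject-years) | n | EAIR per 100 | Limits as written | Limits × 100 |
|---|---|---|---|---|---|
| A | 20.7 | 0 | 0 | 0 to 0.18 | 0 to 17.8 |
| A | 11.6 | 0 | 0 | 0 to 0.32 | 0 to 31.9 |
| A | 20.7 | 1 | 4.8 | 0.001 to 0.27 | 0.12 to 26.9 |
| A | 11.6 | 1 | 8.6 | 0.002 to 0.48 | 0.22 to 48.1 |
| A | 20.7 | 5 | 24.2 | 0.078 to 0.564 | 7.84 to 56.4 |
| B | 10.3 | 0 | 0 | 0 to 0.36 | 0 to 35.6 |
| B | 5.8 | 0 | 0 | 0 to 0.64 | 0 to 63.7 |

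**The case against.** The strongest reply is that this is a slip of wording. The section says the intervals are for the EAIR, which it has just put on a 100 subject-year scale, so a careful programmer would supply the factor. If not, the output would give it away. A term normally appears in a table because at least one subject had it, so a zero cell in one arm usually sits beside a cell with n ≥ 1 whose interval visibly misses its estimate. One formula fills both cells, so correcting one corrects the other.

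Much of this stands. The intended scale is probably that of the EAIR, and the error would probably be noticed. The zero cells go unprotected mainly in fixed summary rows that can be empty in every column, such as the row for any anaphylactic reaction (SAP 14.6.7), and even there the overall TEAE table could expose the problem. But the operation actually specified is division alone, and a SAP meant to contain everything needed for the analysis should not rely on its users to correct a formula.

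Two limits on reach also stand. Section 11.2.3 asks for the rates in the ADA-stratified and AESM tables without saying that intervals will be printed, so those tables are affected only where intervals are shown. Serious infections have no table of their own (SAP 14.6.2.1: "no separate summary tabulations will be presented").

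The exposures above are also not bounds. Up to 10 withdrawn subjects may be replaced (Protocol Section 6.5), which can raise exposure. Early withdrawals and cutting exposure at onset can lower it. The factor of 100 depends on none of this.

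**Conclusion.** The concern holds. As written, the limits for the EAIR are exactly 100 times too small relative to the estimate they accompany. That follows from the text alone; the subject-year figures rest on assumed event counts, planned arm sizes and idealised follow-up, and serve only as illustration. The definite effect is on the EAIR intervals in the overall TEAE table. The practical weight is moderate, because the study is not powered for conclusive safety analysis (SAP 2.4). It should still be corrected, since it is a wrong rule for the only measure of uncertainty attached to these rates.

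**What to change.** Replace the scaling sentence in SAP Section 11.2.2 with wording such as: *Both limits from equation [14] will be multiplied by 100 and divided by the total exposure at risk used for the corresponding EAIR, so that estimate and limits are per 100 subject-years; the lower limit is 0 when n = 0.* Tying the denominator to the corresponding EAIR also covers the All Subjects column and the ADA strata. The clause for n = 0 only settles a case in which equation [14] has zero degrees of freedom.

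The cost is one sentence, with no change to data, point estimates or table layout. Under SAP Section 1, a changed definition needs a SAP amendment if the database is not yet locked. If it is already locked, the corrected scaling should be stated in the clinical study report and any intervals already produced should be checked against it.

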11.2.3 Presentation of adverse events

An overview of the number and percentage of subjects who experience TEAEs will be presented by treatment group (including All Subjects), based on the SS. This tabulation will include the number and percentage of subjects with any TEAEs, serious TEAEs, related TEAEs, discontinuation due to TEAEs, severe TEAEs, AEs leading to death and TEAEs leading to death; event counts will also be included. The tabulation will be repeated for Treatment Period TEAEs and Overall TEAEs.

In addition, the following summaries will be presented by treatment group (including All Subjects), SOC, high level term (HLT) and PT, based on the SS:

- Incidence of TEAEs during Treatment Period
- Incidence of TEAEs Overall
- Incidence of serious TEAEs during Treatment Period
- Incidence of serious TEAEs Overall

-
- Incidence of non-serious TEAEs during Treatment Period
 - Incidence of non-serious TEAEs Overall
 - Incidence of TEAEs during Treatment Period by relationship
 - Incidence of TEAEs Overall by relationship
 - Incidence of TEAEs during Treatment Period by maximum relationship
 - Incidence of TEAEs Overall by maximum relationship
 - Incidence of TEAEs during Treatment Period by maximum intensity
 - Incidence of TEAEs Overall by maximum intensity
 - Incidence of fatal TEAEs during Treatment Period by relationship
 - Incidence of fatal TEAEs Overall by relationship
 - Incidence of non-serious TEAEs during Treatment Period by relationship
 - Incidence of non-serious TEAEs Overall by relationship
 - Incidence of serious TEAEs during Treatment Period by relationship
 - Incidence of serious TEAEs Overall by relationship
 - Incidence of non-serious TEAEs during Treatment Period above threshold of 5% of subjects
 - Incidence of non-serious TEAEs Overall above threshold of 5% of subjects
 - Incidence of non-serious TEAEs during Treatment Period above threshold of 5% of subjects by relationship
 - Incidence of non-serious TEAEs Overall above threshold of 5% of subjects by relationship
 - Incidence of TEAEs during Treatment Period by SOC and PT (including the number and percentage of subjects and individual subject numbers/reported terms for each PT stratified by intensity, relationship and seriousness)
 - Incidence of TEAEs (including all TEAEs during Treatment and Post-Treatment Periods) by SOC, HLT and PT and including the EAIR and EAER calculated as described in [Section 11.2.2](#)
 - Incidence of TEAEs (including all TEAEs during Treatment and Post-Treatment Periods) by SOC, HLT and PT and including the EAIR and EAER, stratified by overall ADA status (positive/negative)

In addition, separate AE summaries by treatment group, SOC, HLT and PT (including all TEAEs during Treatment and Post-Treatment Periods combined) will be included for the following AEs of special monitoring (AESM):

- Major cardiovascular events
- Serious infections, including opportunistic infections and tuberculosis (TB)
- Malignancies including lymphoma

- Cytopenias
- Neuropsychiatric events (in particular, depression and suicide)
- Inflammatory bowel disease
- Anaphylactic reaction (hypersensitivity and anaphylactic reactions)
- Hepatic events and drug-induced liver injury

All summary tables (including those for AESM) will contain the number and percentage of subjects and the number of events where applicable. A subject who has multiple events in the same SOC, HLT and PT will be counted only once in the subject counts but all events will be included. In addition, for all tabulations of AESM, the EAER and EAIR will be reported.

The criteria for identifying AESM and additional criteria for reporting AESM are provided in [Section 14.6](#).

In summaries including relationship to IMP, the following relationship categories will be included:

- Related
- Not related

Subjects who experience the same event multiple times will be included in the most related category for tabulations by maximum relationship. Events with missing relationship will be considered as 'Related' for summary purposes but shown as missing in the data listings.

In summaries including intensity, the following categories will be summarized:

- Mild
- Moderate
- Severe

Subjects who experience the same event multiple times will be included in the most severe category for tabulations by maximum intensity. Events with missing intensity will be considered as severe for summary purposes. All data will be presented as recorded in the database for the listings.

Adverse event summaries will be ordered by alphabetical SOC, alphabetical HLT within SOC and decreasing frequency of PT in the 'BKZ 320mg' (Treatment arm B) column for tables including event counts. For tables including only number and percentage of subjects, summaries will be ordered by alphabetical SOC, alphabetical HLT within SOC and decreasing incidence of PT within HLT and SOC in the 'BKZ 320mg' (Treatment arm B) column.

Listings will be presented by treatment group and subject for all AEs, serious adverse events (SAEs), AEs leading to death and AEs leading to discontinuation. Listings will include the onset date/time and outcome date/time of the event (including relative days), the AE duration (derived), days since first dose of IMP, days since most recent dose of IMP, pattern of event, intensity, relationship, action taken and outcome. In addition the listing will flag AEs that led to discontinuation, TEAEs (including classification as 'Treatment Period' and 'Post Treatment' TEAEs), AESM, AEs of special interest (as reported on the CRF) and SAEs.

All AE listings will be based on all subjects screened (ES). A glossary of all TEAE terms will be provided including the SOC, HLT, PT and reported term.

11.3 Clinical laboratory evaluations

Laboratory data (clinical chemistry, hematology, and urinalysis) and changes from Baseline (if applicable) for numeric variables will be listed by treatment group and visit. Any laboratory variables with values that are BLQ or ALQ will be handled as described in [Section 4.2.2](#) for calculation of changes from Baseline and for summary tables. Values outside the reference range for the numeric variables will be flagged in the listings and in addition, will be listed separately. The reference ranges will also be reported in the listings.

Clinical chemistry and hematology variables will be summarized by treatment group (including All Subjects) at each visit, for both absolute values and changes from Baseline.

Laboratory variables will be grouped according to the laboratory function panel and categorized as normal, high or low, if applicable, based on the reference range supplied by the analytical laboratory. For selected variables that are identified in [Table 11-1](#), the change in category from Baseline will be presented in shift tables at all post-Baseline visits.

The number and percentage of subjects with treatment-emergent markedly abnormal (TEMA) laboratory results (to match the TEAE definition stated in [Section 11.1.3](#)) will be tabulated by treatment group and visit. Markedly abnormal laboratory values will be defined as those categorized as Grade 3 and above based on the ranges defined as per the Common Terminology Criteria for Adverse Events (CTCAE) Version 4.03 (2016). These are provided in [Table 14-4](#). The tabulation will include a category for the incidence of TEMA results over all visits which will also count unscheduled measurements.

In addition, for absolute neutrophil count (ANC), all grade 2 CTCAE abnormalities ($<1.5 - 1.0 \times 10^9/L$) will be listed separately, with results from all visits for any subject that has any grade 2 abnormality.

Laboratory measurements meeting the criteria for TEMA will be listed separately for hematology and chemistry. The listings will include all measurements for any variable with at least one TEMA result for each subject.

Any additional laboratory variables not included in the outputs described previously will be listed separately. These will include the following:

- Serology
- Pregnancy tests (serum and urine)
- Follicle stimulating hormone (FSH) (only for postmenopausal women)

The results of the Quantiferon TB Gold test will be listed separately.

Subjects with treatment-emergent liver function test abnormalities at any post-Baseline visit will be summarized (number and percentage of subjects) by treatment group. The criteria for this tabulation are presented in [Section 14.5](#).

Table 11–1: Clinical laboratory measurements

Category	Panel	Variable
Serology	Serology	HIV1-Ab, HIV2-Ab, HBsAg, anti-HBc, anti-HBs, anti-HCV-Ab, TB
Hematology	Red blood cell	RBC count ^a , hemoglobin, hematocrit
	Red blood cell indices	MCH, MCHC, MCV
	Platelet	Platelets
	White blood cell	WBC count ^a
	White blood cell differential	Absolute counts: ANC ^a , basophils, eosinophils, ALC, monocytes, atypical lymphocytes (if indicated) Percentages: neutrophils/leukocytes, basophils/leukocytes, eosinophils/leukocytes, lymphocytes/leukocytes, monocytes/leukocytes.
Chemistry	Electrolytes	Sodium, chloride, potassium, calcium, magnesium
	Kidney function	BUN, creatinine
	Liver function	AST ^a , ALT ^a , GGT ^a , ALP ^a , LDH ^a , total bilirubin (direct bilirubin, indirect bilirubin, if indicated)
	Lipids	Total cholesterol ^a
	Metabolic function	Glucose
	Hormones	FSH ^b
	Fertility	Pregnancy test ^c
	Other	CRP
Urinalysis	Dipstick	pH, protein, blood, leukocyte esterase, nitrite, glucose

Table 11–1: Clinical laboratory measurements

Category	Panel	Variable
	Urine sediment (if indicated)	WBC, RBC, epithelial cells (squamous, transitional and renal tubular), hyaline casts, WBC casts, RBC casts, waxy casts, granular casts, calcium oxalate crystals, uric acid crystals, triphosphate crystals, yeast, bacteria, amorphous urates, amorphous phosphates

ALC=absolute lymphocyte count; ALP=alkaline phosphatase; ALT=alanine aminotransferase; ANC=absolute neutrophil count; AST=aspartate aminotransferase; BUN=blood urea nitrogen; CRP=C-reactive protein; FSH=follicle stimulating hormone; GGT=gamma glutamyltransferase; anti-HBc= hepatitis B core antibody; anti-HBs=hepatitis B surface antibody; HbsAg=hepatitis B surface antigen; HCV-Ab=hepatitis C virus antibody; HIV1-Ab=human immunodeficiency virus 1 antibody; HIV2-Ab= human immunodeficiency virus 1 antibody; LDH=lactate dehydrogenase; MCH=mean cell hemoglobin; MCHC=mean cell hemoglobin concentration; MCV=mean cell volume; RBC=red blood cell; TB=tuberculosis; WBC=white blood cell.

^a Shift tables will be presented for these variables.

^b FSH performed on postmenopausal females who have been postmenopausal for ≥ 1 year and last menstrual cycle occurred < 2 years ago.

^c Pregnancy testing will consist of serum testing at the Screening and SFU visits. The pregnancy test will be urine at all other visits and will be performed locally. If the subject is entering the extension study, a urine pregnancy test will be performed at SFU.

